9.4.4 SAFETY ANALYSES

All candidates who were subjected to the device with Airmod and Capnostream™35 will be included in the safety analyses (performed in the Safety population) and data will be summarized using descriptive statistics. By reporting the numbers of adverse events (AE)/severe adverse events(SAE) within the trial to indicate the incidence rate of safety issues. We will also present the total number of patients suffering from AE/SAE and its percentage of all population.

The incidence of adverse events will be tabulated, summarized by intensity and relationship to the investigational product.

Details refer to the SAP.

9.4.5 BASELINE DESCRIPTIVE STATISTICS

Demographic data, physical examination, vital signs, the administered anesthetic medication and dosage, surgery type, start and stop time of surgery will be summarized. For continuous demographic variables, results will be summarized and presented as N, mean, SD, median, and minimum and maximum values. For categorical (nominal or ordinal) variables, the number and percentage of subjects will be used. No statistical testing will be performed.

9.4.6 PLANNED INTERIM ANALYSES

In the non-blinded total of 300 subjects enrolled, the interim analysis will be performed at the enrollment of 150 subjects (at least 30 non-anesthesia patients enrolled) during the study period. at the nominal significance level using OBrien-Fleming to determine $\alpha=0.00153$. The final analysis will be performed at the end of 300 subjects enrolled. The nominal significance level is using OBrien-Fleming to determine $\alpha=0.02450$.

9.4.7 SUB-GROUP ANALYSES

The primary endpoint will be analyzed based on different subgroups; details are described on SAP.

9.4.8 TABULATION OF INDIVIDUAL PARTICIPANT DATA

No individual participant data will be listed by measure and time point.

10 SUPPORTING DOCUMENTATION

10.1 ABBREVIATIONS

AE	Adverse Event
AirRR	Airmod-scored auscultation sound generated from AS-101
BMI	Body Mass Index
bpm	breaths per minute
CapRR	Machine-scored Capnography (CapRR) generated from CapnostreamTM35 (K150272, Medtronic)
CE	Communate Europene
CFR	Code of Federal Regulations
CONSORT	Consolidated Standards of Reporting Trials
CRF	Case Report Form
DBP	Diastolic Blood Pressure
DSMB	Data and Safety Monitoring Board
EC	Ethics Committee
EMS	Emergency Medical Service
EtCO2	End-tidal Carbon Dioxide
FDA	Food and Drug Administration
GCP	Good Clinical Practice
GLP	Good Laboratory Practices
GLP	Good Laboratory Practice
GMP	Good Manufacturing Practices
ICF	Informed Consent Form
ICH	International Council for Harmonisation of Technical Requirements for Pharmaceuticals for Human Use
IP	Investigational Product
IRB	Institutional Review Board
ISO	International Organization for Standardization
ITT	Intention-To-Treat
IVG	Intravenous General Anesthesia
LOA	Limits of Agreement
MHLW	Ministry of Health, Labour and Welfare
ManARR	Manual-scored auscultation sound originated from AS-101
ManCRR	Manual-scored Capnography (ManCRR) originated from CapnostreamTM35 (K150272, Medtronic)
NOR	Non-operating Room
OR	Operating Room
PACU	Post Anesthesia Care Unit
PADSS	Post Anesthetic Discharge Scoring System
PAR	Post Anesthetic Recovery
PI	Principal Investigator
PMDA	Pharmaceutical and Medical Devices Agency
PP	Per Protocol
QC	Quality Control
RMSD	Root Mean Square Difference
RR	Respiratory Rate
SAE	Serious Adverse Event
SAP	Statistical Analysis Plan
SBP	Systolic Blood Pressure
SoA	Schedule of Activities
SOP	Standard Operating Procedure
TFDA	Taiwan Food and Drug Administration
USADE	Unanticipated Serious Adverse Device Effect
US	United States
WMA	World Medical Association

10.2 SUPPLEMENTARY

10.2.1 PATIENT MONITORING PERIOD (TIME FRAME)

Device installation is done in the preparation period and trial will start upon sedation until discharge from the post-anesthesia care unit (PACU). A small group of patients (at least 40 patients) will also be evaluated for 15 to 30 minutes prior sedation or past discharge.

Location	Preanesthesia Evaluation	Preprocedural Patient Preparation	Sedative/Analgesic medication induction	Intraoperation	Post anesthesia care unit (PACU)
OR	Enrollment	Device installation / Preparation	Trial period ^{1*}	Trial period	Trial period ^{2*}
NORA	Enrollment	Device installation / Preparation	Trial period ^{1*}	Trial period	Trial period ^{2*}
Location	Preanesthesia Evaluation	Non-anesthesia state			Eligible to discharge
Prep room, PACU	Enrollment (40)	Device installation and Trial period for 15~30 minutes			Device installation and Trial period for 15~30 minutes

1* Notice : We included sedative/analgesic medical intended for general anesthesia and not intended for general anesthesia.

2* Notice : We followed the guidance that Patients receiving moderate procedural sedation may continue to be at risk for developing complications after their procedure is completed. Slow drug elimination may contribute to residual sedation and cardiorespiratory depression during the recovery period. Therefore, we proposed to track the recording until patient for fill the discharge requirement.

10.2.2 STUDY POPULATION

The population will be consisted with the study, to cover a wide range of health conditions, comorbidity, and risk, we proposed to enroll at least 40 non-anesthesia patients in a total of 300 sedative/ anesthesia patients from pre-anesthesia evaluation clinics.

10.2.3 INCLUSION CRITERIA

The compared digital stethoscope, AS-101, is not limited to patient age.

We will include patients eligible for procedure sedation/analgesia and have the target level from minimal to moderate and deep sedation/ analgesia. The enrolled patients' pre-anesthesia evaluation (followed ASA guidance) and their medical history will be recorded. We will also ensure that the patient group is wide enough to cover various common medical disorders.

Table 1. Continuum of Depth of Sedation, Definition of General Anesthesia, and Levels of Sedation/Analgesia

	Minimal Sedation (Anxiolysis)	Moderate Sedation/Analgesia (Conscious Sedation)	Deep Sedation/Analgesia	General Anesthesia
Responsiveness	Normal response to verbal stimulation	Purposeful* response to verbal or tactile stimulation	Purposeful* response after repeated or painful stimulation	Unarousable, even with painful stimulus
Airway	Unaffected	No intervention required	Intervention may be required	Intervention often required
Spontaneous ventilation	Unaffected	Adequate	May be inadequate	Frequently inadequate
Cardiovascular function	Unaffected	Usually maintained	Usually maintained	May be impaired

Minimal Sedation (Anxiolysis) indicates a drug-induced state during which patients respond normally to verbal commands. Although cognitive function and coordination may be impaired, ventilatory and cardiovascular functions are unaffected. Moderate Sedation/Analgesia (Conscious Sedation) indicates a drug-induced depression of consciousness during which patients respond purposefully* to verbal commands, either alone or accompanied by light tactile stimulation. No interventions are required to maintain a patent airway, and spontaneous ventilation is adequate. Cardiovascular function is usually maintained. Deep Sedation/Analgesia is a drug-induced depression of consciousness during which patients cannot be easily aroused but respond purposefully* after repeated or painful stimulation. The ability to independently maintain ventilatory function may be impaired. Patients may require assistance in maintaining a patent airway, and spontaneous ventilation may be inadequate. Cardiovascular function is usually maintained. General Anesthesia is a drug-induced loss of consciousness during which patients are not arousable, even by painful stimulation. The ability to independently maintain ventilatory function is often impaired. Patients often require assistance in maintaining a patent airway, and positive pressure ventilation may be required because of depressed spontaneous ventilation or drug-induced depression of neuromuscular function. Cardiovascular function may be impaired.

Because sedation is a continuum, it is not always possible to predict how an individual patient will respond. Hence, practitioners intending to produce a given level of sedation should be able to rescue patients whose level of sedation becomes deeper than initially intended. Individuals administering Moderate Sedation/Analgesia (Conscious Sedation) should be able to rescue patients who enter a state of Deep Sedation/Analgesia, whereas those administering Deep Sedation/Analgesia should be able to rescue patients who enter a state of General Anesthesia. (Developed by the American Society of Anesthesiologists: Approved by ASA House of Delegates on October 13, 1999 and last amended on October 15, 2014. Available at: <http://www.asahq.org/quality-and-practice-management/practice-guidance-resource-documents/continuum-of-depth-of-sedation-definition-of-general-anesthesia-and-levels-of-sedation-analgesia>. Accessed on August 21, 2017.)

*Reflex withdrawal from a painful stimulus is NOT considered a purposeful response.

10.2.4 EXCLUSION CRITERIA

Patients with advanced airway management equipment will be excluded. (For instance, Supraglottic airway device, LMA, Endotracheal tube.)

Some equipment, such as High Flow Nasal Cannula (HFNC), CPAP, suction machine, could continually make noise in the patient's airway, affecting auscultation and RR measurement. These conditions will also be excluded.

10.2.5 INTENDED FOR USE

The Airmod is an Android based software intended to be used with a legally marketed digital stethoscope as input sensor for the continuous, non-invasive monitoring of respiratory rate (RR) in patients aged 20 years and older who are subjected to procedural sedation in which the depth of sedation ranges from minimal to moderate and deep sedation/anesthesia. It is intended for use by healthcare professionals in hospitals and healthcare facilities performing procedural sedation/anesthesia.

10.2.6 SAP ABSTRACT

[figure not shown]
The primary objective is evaluating the non-inferiority of Airmod to Capnostream™35 for respiratory rate monitoring and user experience clinical evaluation, these results will be included in the clinical study report. In a total of 300 patients enrolled, Airmod and Capnostream™35 recorded the respiratory rate concurrently. The demographic of patients and their Charleson comorbidity in the statistical analysis are collected to describe the patient population in our study. We will further analyze the primary and secondary end goal in the records to show non-inferiority of respiratory rate estimation, agreement, and the excellence event detection of Airmod to Capnostream™35. The subgroup analysis in each period and particular BMI patient group will indicate the statistical power of our study and provide further information on the substantial equivalence performance in

respiratory rate measurement. We will also record all the adverse events during the procedure for analysis of device-related hazards or adverse events for the submission documents.

10.2.7 EXAMPLES OF EXCLUDED MEASUREMENT

[figure not shown]
The principle of exclusion is based on the failure event/period of Airmod or Capnostream™35 reported by investigator. Events such as EtCO₂ oversaturated period of Capnostream™35 or noises unable to be eliminated by the noise-cancelling technology and bias the respiratory rates. The report will be confirmed by the principal investigator, data apart from these events is still included.

EtCO₂ oversaturated period of Capnostream™35:

*ORS: Operation start; EHV: Patient exhausting voice; EMF: Capnostream™35 failure determined by Investigator

Noises unable to be eliminated by the noise-cancelling technology and bias the respiratory rates:

*PAM: Patient movement; BDM: Sickbed movement start; FCV: Friction voice; BDE: Sickbed movement end; AAV: Abnormal acoustic sound produced by upper GI endoscope.

10.3 PROTOCOL AMENDMENT HISTORY

Version	Date	Description of Change	Brief Rationale
3.0	2021/10/1	Minor fixed of description (no effect with study design) and added supplementary section (10.2).	Found some description errors (no effect with study design). Meanwhile, give further information to complement the protocol.

A 5x5 grid with a large red 'X' drawn through it. The word "HEROIC" is written vertically along the top edge, and "MEDICAL" is written diagonally across the bottom-left corner. The word "FAITH" is written vertically along the right edge.

| PACU | Post Anesthesia Care Unit | |
| PADSS | Post Anesthetic Discharge Scoring System | |
| PAR | Post Anesthesia Recovery | |
| SAE | Serious Adverse Event | |
| SAP | Statistical Analysis Plan | |

Table 1. Abbreviations and Definitions

4 Introduction

4.1 Preface

Airmod is a software application designed to aid healthcare professionals by monitoring a patient's breathing in real time. It can detect inhalation acoustic sound and provides respiratory rates based on the analysis of the acoustic signals of breathing sounds collected by the electronic stethoscope. This is an observational, prospective, multi-center, pivotal study.

4.2 Scope of the analyses

These analyses will evaluate the non-inferiority of Airmod to Capnostream[™]35 for respiratory rate

monitoring and user experience clinical evaluation, the results will be included in the clinical study report.

4.3 Study Objectives

The objective of this study is to demonstrate that the performance and safety of Airmod in monitoring respiratory rate is non-inferior to Capnostream[™]35.

Primary Objective:

To evaluate accuracy and performance of respiratory rate (RR) measurement from Airmod compared to Capnostream[™]35. The primary objective is to establish the non-inferiority.

Secondary Objectives:

1. To assess the accuracy of respiratory rate measurement by Airmod in comparison with manual-scored auscultation sound during the less sensitive period of Capnography on Capnostream[™]35.

2. To measure the agreement between AirRR and ManCRR.

3. To evaluate the response time of the first breath detection followed by administration of jaw thrust during the apnea period. The 3 secondary objective is to compare the response time of Airmod versus Capnography.

4. To compare the influence of subjects to variated breath rates on respiratory rate monitoring in bpm as measured by Airmod, manual-scored and Capnostream[™]35.

5. To evaluate the safety and usability of Airmod.

Manual-scored Capnography (ManCRR) originated from Capnostream[™]35 (K150272, Medtronic) Machine-scored Capnography (CapRR) generated from Capnostream[™]35 (K150272, Medtronic) Manual-scored auscultation sound (ManARR) originated from AS-101 Airmod-scored auscultation sound (AirRR) generated from AS-101

4.4 Endpoints

Primary Endpoint:

The difference between AirRR and ManCRR, which is greater than -3 establishes non-inferiority. The unit in this calculation is bpm and sampling rate is 1 Hz.

Secondary Endpoints:

1. The accuracy of inhalation classification in the segmentation basis is greater than 82.5% at the 95% Cl. The performance metrics (F1-socre, MAPE) at event level will be demonstrated and target for F1-score > 0.8, MAPE < 0.5.

2. To measure the agreement of AirRR and ManCRR on concordance correlation coefficient, and on their mean and bias by Bland-Altman analysis.

3. Use paired t-test to compare the response time of Airmod versus Capnography on Capnostream[™]35 after administration of jaw thrust. In the target of p<0.05 indicates significance.

4.1. The difference of ManCRR minus AirRR and ManCRR minus CapRR indicates non-inferiority at margin of 3 bpm (M1) and sampling rate 1Hz.

4.2. The difference of ManCRR minus AirRR and ManCRR minus CapRR indicates non-inferiority at margin of 2 bpm (M2) and sampling rate 1Hz.

5. The absence of unanticipated serious adverse device effect (USADE) during study period and the questionnaire.

Evaluating the Non-Inferiority of Airmod to Capnostream™35 on Respiratory Rate Monitoring and User Experience Clinical Evaluation

[Time Frame:

Non-Anesthesia Stage: Up to 40 patients will be randomly assigned to non-anesthesia stage assessment, the measurement will be evaluated after enrollment with ICF, at the non-operating room (NOR) area. (5~30 minutes)

Procedure Stage: From firstly anesthetic administration to end of procedure. (Depends on procedure 10mins ~ few hours)

Transportation Stage: During transportation of subjects. (1~10 minutes)

Post anesthesia care unit stage : From subjects arrive post anesthesia care unit (PACU) to discharge from PACU (PAR or PADSS score \geq 9) (At least 15 minutes)]

5 Study Methods

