9 STATISTICAL CONSIDERATIONS

9.1 STATISTICAL HYPOTHESES

Primary Analysis:

In this study, all the measurements were conducted in the same subject, and the clocking variance would be limited by investigator justification procedure to acquire the utmost matching recording. The study design is a paired non-inferiority test to evaluate accuracy and performance of respiratory rate (RR) measurement from Airmod compared to Capnostream™35. The primary objective is to establish the non-inferiority. The primary end goal is to test the entire effect at the margin of 3 breaths per minute (bpm). The non-inferiority is a directional (one-sided) test. The null hypothesis (H_0) and alternative (H_1) are defined as:

$$H_0: \mu_{\text{AirRR}} - \mu_{\text{ManCRR}} < -3; \\ H_1: \mu_{\text{AirRR}} - \mu_{\text{ManCRR}} \geq -3.$$

Details refer to the SAP.

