9.4.2 ANALYSIS OF THE PRIMARY EFFICACY ENDPOINT(S)

In this study, all the measurements were conducted in the same subject, and the clocking variance would be limited by investigator justification procedure to acquire the utmost matching recording. The study design is a paired non-inferiority test to evaluate accuracy and performance of respiratory rate (RR) measurement from Airmod compared to Capnostream™35. The primary objective is to establish the non-inferiority. The primary end goal is to test the entire effect at the margin of 3 breaths per minute (bpm). The non-inferiority is a directional (one-sided) test. The null hypothesis (H0) and alternative (H1) are defined as:

$$\begin{aligned} H_0: \mu_{\text{AirRR}} - \mu_{\text{ManCRR}} &< -3; \\ H_1: \mu_{\text{AirRR}} - \mu_{\text{ManCRR}} &\geq -3. \end{aligned}$$

At the interim analysis, under 99.69% CI, when reject the null hypothesis (H0) indicates the non-inferiority.

At the final analysis, under 95.1% CI, when reject the null hypothesis (H0) indicates the non-inferiority.

A subgroup analysis for those subjects with $\text{BMI} \geq 30$ will follow the original study design in a stratified sample pool to test the non-inferiority at the margin of 3 bpm.

According to 7.2, part of the measurement result within subject will be censored and excluded in the paired non-inferiority test. The principle of exclusion is based on the investigator reported failure event/period of Airmod or Capnostream™35, the report will be confirmed by the principal investigator. The data prior to discontinuation or following a fixed machine failure period will be included in the paired non-inferiority test.

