The primary efficacy analysis of primary endpoints are comparing the difference of AirRR and ManCRR to reject the null hypothesis (difference of estimation is greater than the non-inferiority limit : -3) under 95% level of confidence interval of all ITT population. The $\mu\alpha$ denotes the respiratory counts of AirRR per minute, and the $\mu\beta$ denotes the respiratory counts of ManCRR per minute. The respiratory count per minute is the mean of recorded samples (eliminating the missing or non-detecting data

point) in each minute. Respiratory counts per minute represent the respiratory rate and are tested in the primary objective hypothesis with the type I error of 0.025, and Type 2 error of 0.2, and the power is 0.8 with single tail non-inferiority analysis.

| Step | Summary |
|-------------------------------|---|
| Objective | Non-inferiority: H0:μα-μβ> d _{NI} vs H1:μα-μβ≤ d _{NI} |
| Endpoint | Margin_1 >-3; Margin_2 >-2 |
| Error | Type I error α=0.025 (one-sided) |
| | Type II errorβ=0.2, Power 1-β=0.8 |
| Non-inferiority limit | d _N = -3 Brpm |
| Population standard deviation | σ=3.29647 |
| Others | r=1, dropout rate=0.3% |

Reference from our pilot study in 25 cases

Table 6. Statistical information referencing from pilot study

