9.1.1 Secondary Analyses of Primary Efficacy Endpoint

The primary efficacy analysis will be further divided into three periods of study 1.Induction (3minutes from DIN), 2.Intraoperative period, 3.PACU period to reveal the performance of our device in particular scenarios. The data will be analyzed on a minute basis, and also aggregated per subject basis in each period. The candidates in the non-anesthesia group will be solely analysis for the whole period to represent the normal patient group in a healthcare facility.

| Look | Info Fraction | Approx. Cum. Subjects | Nominal Significance Level (1-sided) | Efficacy Boundaries z-scale |
|---------|---------------|-----------------------------|--|-----------------------------------|
| Interim | 50% | 150 | 0.00153 | 2.9626 |
| Final | 100% | 300 | 0.02450 | 1.9686 |

Fig 6. Information of Interim analysis

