the actual measurement of the respiratory event.

9.2.2 Analysis to measure the agreement between AirRR and ManCRR.

Bland Altman analysis, and concordance correlation is adopted to measure the agreement between AirRR and ManCRR. The quantitative results of respiratory rate from these devices under test over time are evaluated by the above mentioned method to analyze the mean and bias from the plot and concordance correlation coefficient.

Fig 9. Bland Altman between AirRR and ManCRR (Example)

Fig 10. Correlation between AirRR and ManCRR (Example)

Fig 11. Correlation between AirRR and ManCRR during induction period (Example)

Evaluating the Non-Inferiority of Airmod to Capnostream™35 on Respiratory Rate Monitoring and User Experience Clinical Evaluation

Fig 12. Correlation between AirRR and ManCRR during Inter-operation period (Example)

Fig 13. Correlation between AirRR and ManCRR during transportation and PACU period (Example)

Also, we apply a sensitivity test for Airmod by comparing the reference method at each time point and calculating the absolute deviations in breaths per minute (bpm). As a measure of accuracy, absolute deviations were calculated as a percent of reference.

Percent absolute deviation were averaged for each subject yielding overall measures of accuracy. To evaluate the accuracy of Airmod, the individual percent absolute deviation was compared for each monitoring time point by subtracting ManCRR from AirRR and then averaged within subject. A paired t test was used to evaluate significance across subjects.

To measure the precision of Airmod for each subject, the standard deviation of percent deviations (in nonabsolute value) was calculated. The precision of Airmod was compared through a paired t test of the subject-specific standard deviations of Airmod's percent deviations from reference.

9.2.3 Analysis to evaluate the response time of the first breath detection followed by administration of jaw thrust during the apnea period. The 3rd secondary objective is to compare the response time of Airmod versus Capnography.

Use paired t-test to compare the response time of Airmod versus Capnography on Capnostream[™]35 after administration of jaw thrust. The target of p<0.05 indicates significance difference.

Evaluating the Non-Inferiority of Airmod to Capnostream™35 on Respiratory Rate Monitoring and User Experience Clinical Evaluation

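### The primary rule limits only the average signed difference, so an uninformative output centred near the patients' mean rate passes almost surely; a pass does not show accuracy

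*SAP*

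**What the plan says.** The primary endpoint (SAP 4.4; the Protocol synopsis and section 3 are nearly identical) is "The difference between AirRR and ManCRR, which is greater than -3 establishes non-inferiority". Protocol 9.1 and 9.4.2 put this as a hypothesis on the mean of AirRR minus the mean of ManCRR against -3 bpm, and Protocol 9.1 adds "The non-inferiority is a directional (one-sided) test". Protocol 9.4.2 describes it as "a paired non-inferiority test to evaluate accuracy and performance of respiratory rate (RR) measurement from Airmod". SAP 9.1 sets "the type I error of 0.025, and Type 2 error of 0.2, and the power is 0.8 with single tail non-inferiority analysis".

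Against the reference signals, accuracy and agreement are assessed in the secondary endpoints:

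- Endpoint 1 has targets: segment accuracy above 82.5%, F1 above 0.8, MAPE below 0.5. The comparison is with ManARR, and only in capnography's less sensitive periods (SAP 4.4, 9.2.1).
- Endpoint 2 is the concordance correlation coefficient (CCC) and Bland-Altman analysis of AirRR against ManCRR. No numerical limit is given. Protocol 9.4.3 judges the differences by whether they lie within the 95% limits of agreement.
- SAP 9.2.2 adds "As a measure of accuracy, absolute deviations were calculated as a percent of reference", averaged per subject, with no threshold.
- Endpoints 4.1 and 4.2 are again written as signed differences, with margins of 3 and 2 bpm.

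Nothing in the available text makes primary success depend on any of these. Part of SAP 9.1 was not available.

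**The concern.** A mean signed difference says whether the device reads high or low on average. It does not say whether it follows the patient. Reading 6 bpm high in half the subjects and 6 bpm low in the other half gives a mean difference of zero. The sponsor recognises this elsewhere: Protocol section 3 and 9.4.3 justify MAPE because it keeps errors of opposite sign from offsetting each other. The primary endpoint lacks that protection.

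Protocol 2.2 argues that rate matters because an abrupt change signals a change in the patient. A display that never changes can meet the primary rule, and SAP 7.5.1 allows early success to be declared on that rule at the interim. At stake is the wording of the main conclusion: a pass would be reported under an accuracy objective that the rule does not test.

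**Working it through.** **Boundaries.** SAP 9.1.1 gives "Interim | 50% | 150 | 0.00153 | 2.9626" and, for the final look, 300 subjects, 0.02450 and z = 1.9686. These reproduce: 1 − Φ(2.9626) = 0.00153 and 1 − Φ(1.9686) = 0.0245. With correlation √0.5 between looks, the overall one-sided error is 0.0250.

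**Inputs.** Margin -3 bpm; n = 150 and 300 from SAP 9.1.1; n = 180 from the Protocol's 40% dropout (300 × 0.6). The direction follows Protocol 9.1, because the table in SAP 9.1 writes H0 and H1 the other way round. The documents give no distribution of patient rates. I assume a normal distribution with mean 15 and SD 3.3, 5 or 7, truncated to 4–35 bpm, with one value per subject. (The SAP comparison table gives 4–35 as the claimed range of the device.)

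**Formula.** For a mean offset b and SD s of the differences, P(pass) = Φ((b + 3)√n / s − z). A fixed output carries no information, so s is simply the SD of the patients' rates and the CCC is 0.

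**Fixed output of 15 bpm.**

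| SD before truncation | Patients' mean, SD | Offset b | n = 150 | n = 180 | n = 300 |
|---|---|---|---|---|---|
| 3.3 | 15.00, 3.29 | 0.00 | 1.00 | 1.00 | 1.00 |
| 5 | 15.18, 4.79 | −0.18 | 1.00 | 1.00 | 1.00 |
| 7 | 15.81, 6.15 | −0.81 | 0.92 | 0.997 | 1.00 |

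For the last row: 2.19 × √150 / 6.15 − 2.9626 = 1.40, so 0.92; 2.19 × √180 / 6.15 − 1.9686 = 2.81, so 0.997; 2.19 × √300 / 6.15 − 1.9686 = 4.20, so 1.00. Simulation agrees within about 0.01 (0.91 at the interim for SD 7). Requiring the upper limit also to be below +3 bpm leaves these probabilities unchanged.

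**How far the average may fall.** Without truncation, a fixed output still passes 95% of the time at n = 300 if b = −3 + (1.9686 + 1.645)s/√300. That is −2.31, −1.96 and −1.54 bpm for s = 3.3, 5 and 7. At b = −3 the pass probability is 0.0245. With truncation, a fixed 13 bpm passes with probability 0.9995 (SD 3.3), 0.84 (SD 5) and about 0.08 (SD 7). A fixed 8 bpm passes with probability 0.00.

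**Would an absolute-error limit of 3 bpm be enough?** Take zero-mean normal differences with SD 3.29647, the value in the SAP 9.1 table (not stated there to be the SD of paired differences). Then E|d| = 0.798 × 3.29647 = 2.63 and SD|d| = 0.603 × 3.29647 = 1.99. The standard error is 1.99/√300 = 0.115. P(upper limit below 3) = Φ((3 − 2.63)/0.115 − 1.9686), about 0.89 at n = 300 (about 0.88 simulated). At n = 180 the standard error is 0.148 and the probability is about 0.70. The fixed 15 bpm output at SD 3.3 has essentially the same error distribution, so it also passes about 88% of the time. At that SD the limit does not tell the two apart.

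**Would a CCC floor of 0 be enough?** With patient SD 3.3, an output with SD 0.5 and correlation 0.2 has CCC = 2 × 0.2 × 3.3 × 0.5 / (3.3² + 0.5²) = 0.06. In simulation at n = 300 it met the 3 bpm absolute limit and a CCC lower limit above 0 together in 89% of trials.

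**The case against.** A reader might infer that any output unrelated to breathing passes. That is not so: the average must lie above the patients' mean or at most about 1 to 2 bpm below it, depending on spread.

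A reader might also cite random output over 4–35 bpm as proof. Its mean is 19.5 bpm, about 4.5 above the assumed patient mean, so it passes because the rule has no upper limit. A ±3 bpm bound would reject it. Only an output centred near the patients' mean isolates the cancellation problem.

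A third inference is that the plan never tests accuracy. It does. Endpoint 1 compares detected inhalations with manual labels in time, and output unrelated to breath timing should fail its F1 target. But it covers only less sensitive capnography periods, uses a different reference, and gates nothing. Its MAPE target is weak: measured against the assumed rates, the fixed 15 bpm output has a MAPE of about 0.20 to 0.40, below 0.5. The Bland-Altman criterion in Protocol 9.4.3 does not help either, because its limits come from the same differences and widen with them.

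Two cautions stand. The rate distribution is assumed, and the unavailable part of SAP 9.1 could hold more detail. The endpoint and the Protocol hypotheses are intact, however, and all agree on a one-sided limit on a mean difference.

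**Conclusion.** The concern holds for the primary rule. As written, that rule tests only the lower side of the mean bias, and an uninformative output averaging near the patients' mean passes with probability 1.00 at 300 subjects, at least 0.99 at 180, and 0.91 to 1.00 at the interim. The figures assume rates centred on 15 bpm with SD 3.3 to 7 and one value per subject. SAP 9.1 uses minute means; treating minutes as independent would shrink the standard error and raise these probabilities. Adding an upper limit on the mean would not cure it. A primary pass therefore supports a statement about average offset, while accuracy rests on secondary endpoints that do not gate success. The documents do not support the wider claims that every unrelated output passes or that accuracy is left out of the plan.

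**What to change.** 1. In SAP 4.4 and 9.1 and Protocol 9.4.2, state that meeting the primary rule supports only the conclusion that the mean offset is no lower than -3 bpm, and not accuracy.
2. Permit an accuracy claim only if the planned AirRR–ManCRR agreement analysis also meets a numerical limit: a lower confidence limit for the repeated-measures CCC well above 0, or prespecified maximum Bland-Altman limits of agreement. A mean absolute difference below 3 bpm should not stand alone.
3. Fix that limit before any paired AirRR–ManCRR results are reviewed. The study is open and SAP 7.5.6 gives interim results to the sponsor and investigators, so this means before the interim.

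Step 1 costs only wording, and the mean-offset conclusion keeps its present power (about 1.00 at zero bias, SD 3.29647 and n = 300). Step 2 uses analyses already planned but makes the accuracy claim harder to reach. The 0.89 and 0.70 shown for an absolute-error limit indicate how much can depend on the limit and the evaluable number, so the sponsor should choose it with 180 to 300 subjects in view.
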